4.6. Data analysis RCT

Continuous data will be presented as median (interquartile range) and dichotomous data as absolute (n) and relative (%) frequencies. Baseline data will be compared group-wise to ascertain successful randomization. Outcome data will be compared group-wise using Chi-square test according to intention to treat (ITT) among all randomized women according to allocation, and per-protocol (PP) according to the intervention women actually received. The risk ratio between groups of our main outcome and 95% confidence interval will be calculated using the STATA csi command.

Based on a previous RCT in the same setting we expect the baseline rate for our main outcome, uptake of LARC after abortion, to be 12%. We hypothesize that the intervention group using TECC will double their uptake of LARC. We also wish to be able to analyze our two study settings independently of each other. To show a doubling of uptake in a study group (effect size or odds ratio 2.0) corresponding to an absolute increase of 12%, with 95% confidence and 90% power we will need to analyze 212 women in each arm. This 95% confidence interval for that risk difference would in that case have a lower margin of 5% increase (corresponding to an OR of 1.5), which in a context of low use is considered clinically significant, i.e., the effect size of the intervention that we consider of clinical importance starts at 5%.

Based on previous studies we estimate that our loss to follow up will be up to 20% at 12 months bringing our sample to 510 women. Accounting for the statistical independency of the South African and Kenyan cohorts we double the sample for a total sample size of 1020 women of which 510 will be recruited in each country. This would give us 80% power and 95% confidence to determine a 12% difference in uptake of LARC in the intervention and control group at 12 weeks.

5. Description of Risks and Benefits

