4.4. Research procedures and data collection methods RCT

4.4.1. Research procedures and data collection methods RCT – all participants

On the day of recruitment, a baseline survey will record participant demographic variables, socio-economic status, reproductive history, prior and current use of contraception, and frequency of use of the internet. Follow up surveys will be conducted 12 weeks, 6 months, and 12 months. Baseline and follow up surveys will be recorded either by women receiving a link to RedCap and filling out the questionnaires on their phones, or through a telephonic interview with the research assistant, depending on participant preference. At baseline, data for accessing the baseline survey on RedCap and using the TECC service will be provided to participants from the study staff by means of data hotspot/WIFI provided from study staff devices. The reimbursement amount will assist participants to cover costs for data required for the follow up survey and any contact with the TECC service after baseline. The participants also have the choice to participate in follow up surveys by phone interview with study staff. The baseline survey is expected to take about 10-15 minutes. The follow up survey at 12 weeks is expected to take about 20-25 minutes and follow up surveys at 6 months and 12 months are expected to take about 5-10 minutes. The questionnaires will capture primary and secondary outcomes as described below.

Outcomes

Primary outcome at 12 weeks

Uptake of LARC, defined as uptake of an IUD or a subdermal implant for contraception, within 12 weeks

Secondary outcomes at 12 weeks

1. choice of LARC

2. uptake of any contraception
3. choice or uptake of new method with regards to previous use
4. satisfaction with TECC service (using a multi-question validated scale)
5. Rated use of service for decision making (using a multi-question validated scale)
6. Degree of agency in decision making (using a multi-question validated scale)
7. preference for counselling

Secondary outcomes at 6 months

1. continued use of LARC
2. continued use of any contraception
3. recurrent unintended pregnancy
4. recurrent abortion

Secondary outcomes at 12 months

1. continued use of LARC
2. continued use of any contraception
3. recurrent unintended pregnancy
4. recurrent abortion
5. Change of method at any timepoint up to 12 months
6. Reason for change of method

Subsidiary outcomes

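### Chi-square is the only between-arm test named for outcome data, and it does not suit the secondary outcomes measured on validated multi-item scales (clearest for decision-making agency)

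*Protocol*

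**What the plan says.** Protocol section 4.6 (Data analysis RCT) first sets the descriptive summaries: "Continuous data will be presented as median (interquartile range) and dichotomous data as absolute (n) and relative (%) frequencies". It then gives the comparison: "Outcome data will be compared group-wise using Chi-square test according to intention to treat (ITT"), with a per-protocol comparison alongside. The only other between-arm quantity in the section is a risk ratio with 95% confidence interval for the main outcome. No test is named for continuous or ordinal data.

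Section 4.4.1 lists among the 12-week secondary outcomes:

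- "satisfaction with TECC service (using a multi-question validated scale")
- "Rated use of service for decision making (using a multi-question validated scale")
- "Degree of agency in decision making (using a multi-question validated scale")

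No scoring rule, cut-point or grouping is given for these scales in the RCT. The grouping of satisfied with very satisfied in section 3.4 belongs to the pilot's compound outcome.

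**The concern.** A median and interquartile range describe a score, but a chi-square test does not compare medians. To use the named test on a scale score, the analyst must either group the score or treat its values as categories without order. Both discard information that the instrument was chosen to provide. If the grouping is not fixed in advance, the result also depends on where the cut falls.

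These comparisons matter to the trial's own aims. Aim 3 in section 1 includes satisfaction, and section 5.2 names dissatisfaction as one of the main ways in which the online service could do worse than standard care. Section 4.3 says that neither the participant nor the research assistant can be blinded, so for self-reported scores the analysis rule should be settled beforehand.

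The protocol states a test here, so this is more than a detail left to a statistical analysis plan. A plan that used a rank test or a linear model for these scales would depart from the literal wording of section 4.6.

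**Working it through.** **Inputs from the protocol.** Section 4.6: control uptake 12%, increase 12 points, 95% confidence, 90% power, 212 analysed per arm, up to 20% loss, 510 women per country. Section 4.3: 1:1 allocation.

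**Assumptions, not in the documents.** The score is roughly normal with equal SD in both arms, the effect is a shift, and tests are two-sided at 5%.

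**1. The plan's own figure.** For 12% against 24% with unpooled variance:

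n = (1.96 + 1.2816)² × (0.12 × 0.88 + 0.24 × 0.76) / 0.12² = 10.507 × 0.288 / 0.0144 = 210.1, so 211 per arm.

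The pooled-variance form gives 214. The stated 212 reproduces. It concerns the binary primary outcome, for which chi-square is suitable. The protocol gives no power figure for the scales.

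**2. Women analysed per arm, one country.** 510 / 2 = 255; 255 × 0.80 = 204.

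**3. Shift with 80% power on the score.** d = (1.96 + 0.8416) × √(2/204) = 0.277 SD.

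**4. Two categories.** Power = Φ{[|p₂ − p₁| − 1.96√(2p̄(1 − p̄)/n)] / √[(p₁(1 − p₁) + p₂(1 − p₂))/n]}, with n = 204.

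- Median split: 50% becomes Φ(0.277) = 60.9%. Power = Φ[(0.1093 − 0.0965)/0.0489] = Φ(0.26) = 60%.
- 80/20 cut: 20% becomes 28.6%, power 53%; or 80% becomes 86.8%, power 46%.

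The large-sample efficiency of a cut at proportion q, relative to the t-test, is φ(z_q)²/[q(1 − q)]. This is 0.637 at the median and 0.490 at 80/20.

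**5. Three to five equal groups, Pearson chi-square.** The noncentrality is (n d²/2) × I_k, with n d²/2 = 204 × 0.277²/2 = 7.85 (unrounded d) and I_k the information kept by k groups.

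| Groups | I_k | Noncentrality | df | Power |
|---|---|---|---|---|
| 3 | 0.793 | 6.23 | 2 | 60% |
| 4 | 0.861 | 6.75 | 3 | 57% |
| 5 | 0.897 | 7.04 | 4 | 54% |

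More groups keep more information, but the unordered test spends it on extra degrees of freedom. A method that used the order of the groups would lose only 10–21% (1 − I_k), but section 4.6 names no such method.

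**6. Both countries pooled.** 2 × 204 = 408 per arm, same shift of 0.277 SD. On the score: Φ(0.277 × √(408/2) − 1.96) = Φ(2.00) = 98%. After a median split: 88%. At 80/20: 75–82%. The efficiencies in step 4 do not change; the larger sample absorbs more of the loss for a shift of this size.

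**The case against.** The strongest reply is that the chi-square sentence may be meant only for the dichotomous outcomes, which make up most of the list in section 4.4.1. On that reading the test for the scales is merely unstated and can be left to a statistical analysis plan, and the median and interquartile range suggest that scores will stay ungrouped. This is a possible intention, but the sentence carries no such limit. It is a good reason to expect that the correction will be uncontroversial.

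Several further points stand and limit the finding:

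- The documents give no score distribution. Skewed or ceiling-limited scores would give other figures. A reader might infer that a third or more of the information is necessarily lost; that holds only under the assumed normal shift, with two categories or an unordered test.
- The 204 per arm is a low figure. The 20% loss is stated for 12 months, whereas the scales are collected at 12 weeks, and nothing rules out a combined analysis of both countries.
- Satisfaction is worded as satisfaction with the TECC service, which has no clear control-arm counterpart; rated use of the service may have the same difficulty. Aim 3 and section 5.2 do intend a between-arm comparison of satisfaction, but as listed only agency is clearly comparable.
- Scoring rules or cut-points may stand in the instruments or in appendices that are not shown. The documents do not support saying that a cut-point would be chosen after seeing the data.

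Two stronger readings fail. One is that chi-square is unreliable for rare events such as recurrent pregnancy: at an assumed 2% rate with 204 per arm, the exact type I error of the uncorrected Pearson test is 4.5%, below the nominal 5%. The other is that binary secondary outcomes get no effect size: section 4.6 promises counts and percentages, from which a risk difference follows, and naming an interval for each secondary outcome is ordinary content for an analysis plan.

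**Conclusion.** The concern holds in a limited form. Section 4.6 fixes one between-arm test without regard to outcome type, and that test does not suit outcomes scored on multi-item scales. The mismatch is clear for agency, and extends to satisfaction and rated use if both arms answer those items.

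Under the assumed normal shift, within one country, 80% power on the score falls to between 46% and 60% across the groupings examined. The consequence is milder if the countries are pooled. The direction of the loss is secure for a score of this kind; the exact figures depend on assumptions that the protocol cannot confirm. The primary outcome, its risk ratio and interval, and the sample size are untouched. The correction is worth making because the secondary comparisons serve a stated aim, but it does not threaten the main result.

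**What to change.** In section 4.6:

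- Restrict chi-square to categorical outcomes.
- Compare each scale on its validated total score, by Wilcoxon rank-sum with a Hodges–Lehmann difference or by a linear model, with a 95% confidence interval. The rank-based option fits the planned median and interquartile range.
- If a grouped version of a scale is also wanted, fix its cut-point in advance.
- State which of the three scales both arms complete, so that it is clear where a between-arm comparison applies.

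This costs a few lines of text and very little extra analysis. It needs no new data and no change to the sample size.

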4.1. Study design RCT

Following the pilot study, we will perform an RCT comparing TECC with standard care contraceptive counseling. The study design of the RCT will adhere to the CONSORT statement for randomized controlled trials for non-pharmacological interventions (15). In line with the theory surrounding controlled investigation into models of care, we include in our outcomes measures of adherence of participants to interventions, a description of attempts to limit bias because blinding will not be possible, and specifications of the delay between randomization and initiation of the intervention. The trial and trial protocol will be registered at clinicaltrials.org and the Pan-African Clinical Trials Registry (PACTR).

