4.3. Recruitment, enrolment, and randomization RCT

Women will be informed about the study either at the abortion clinic (South Africa) or by phone through the collaborating abortion care hotline Reproductive Health Network Kenya (RHNK). All women in the South African arm of the study will be informed about the study while waiting to be seen for a consultation at the abortion clinics on a recruitment day. Interested women will be screened for eligibility. Eligible women will be recruited to the study after going through a private informed consent procedure with study staff.

Participants will be randomly allocated 1:1 to either TECC or in-person contraceptive counseling. The randomization sequence will be computer-generated 1:1 in permuted blocks of varying sizes by a researcher not involved in data collection and imported into the electronic research data capture tool RedCap. A research assistant will perform the randomization, in the presence of the participant on the same day as the intervention, by clicking on a link in the RedCap system which generated the next sequential number according to central allocation. Blinding of either the research assistant or participant to group allocation will not be possible.

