4.4.2. Research procedures and data collection methods RCT – Intervention group

The intervention will consist of online contraceptive counseling - TECC. On the day of the abortion, while waiting for their abortion consultation with the clinic nurse, participants will use their phones to complete a contraceptive counseling session through the TECC service. At baseline, data for using the TECC service will be provided to participants from the study staff by means of data hotspot/WIFI provided from study staff devices.

Participants will be informed and guided to their method of choice based on their reported preferences, reproductive history, and health conditions. The TECC will be designed to be interactive, i.e., provide a personalized path through contraceptive counseling the content of which depends on the individual needs and preferences of the participant.

After completing a counseling session, participants in the TECC group will receive an online medical certificate certifying that she has received professional contraceptive counseling and, if no contraindications to use exist, that she's eligible for the method of

her choice. If she has a medical condition that requires examination prior to prescription her certificate will indicate that she must see a nurse prior to initiation of her method. Depending on her choice, she will then be directed with this certificate to the nearest clinic for initiation of the method (intrauterine device, progestin injectable, or progestin implant), or to a pharmacy to pick up her method (progestin-only pill, combined oral contraceptive pill. In Kenya, women will receive home distribution or distribution to a local pick-up point, through our partner organization and distributor of contraceptives Triggerise.org. A question in the TECC chat will allow participants to ask the TECC backoffice (study doctor) to contact them for further support. The chat algorithm will also automatically alert the study doctor in case of a severe liver disease or cancer, which would require further attention.

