4.4.3. Research procedures and data collection methods RCT – comparison group

The control group will receive in-person contraceptive counselling information and initiation at the clinic where they perform the abortion (South Africa) or a clinic to which they are directed by the abortion care hotline (Kenya). Mode of contraceptive counseling may vary between clinics but the routine procedure at each clinic will be documented in the study. To keep the study as close to clinical practice as possible we will not modify the care received by the control group by standardizing the counseling delivered at the clinics.

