5.3. Minimizing risk

Study procedures have been designed to minimize the risks of the intervention while not impacting on the accurate assessment of the study question.

- The format and content of the online service will be adapted specifically to the women in the study setting. The service will be developed according to the principles of human centered design which means involving end users/representatives of the study population already in the development of the service.
- The service will be tested in a pilot study designed to assess usability and acceptability for our patient group as a part of pre-trial procedures.
- If the participant is unable to complete the online counseling, she will cross over to the other arm of the study and receive standard contraceptive counseling.
- Eligibility screening will be done by the study doctor and the study Co-PI.
- The study doctor will be responsible for completing the medical records for the telemedicine group of patients so that participating clinics will have a physical record of the participants visit.

- Study participants in the TECC arm will have access to an online helpdesk, staffed by the study doctor, as part of the TECC service.
- Participants in the study will be of adult age and have unimpaired ability to understand and read one of the languages in which the intervention is delivered.
- Participants in the study setting will predominantly have low financial means but will have good access to emergency care services.
- Participants will be followed up after during the study period
- Participants will have constant access to study staff by telephone if necessary but will be instructed to contact public health care or the TECC helpdesk primarily.

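### The analysis labelled per-protocol groups women by counselling received, which is as-treated, and with the cross-over rule it would count some TECC women as controls

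*Protocol*

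**What the plan says.** Protocol section 4.6 sets two group-wise comparisons of the outcomes side by side. The first is "intention to treat (ITT) among all randomized women according to allocation". The second is "per-protocol (PP) according to the intervention women actually received". The section gives no adherence criterion and no exclusion rule for the second comparison, and none appears elsewhere in the Protocol.

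Section 5.3, in its list of measures to reduce risk, states: "If the participant is unable to complete the online counseling, she will cross over to the other arm of the study", where she receives standard counselling. Section 4.4.3 makes in-person clinic counselling the care of the comparison group.

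Two other places bear on whether receipt of counselling will be known. Section 4.1 says "we include in our outcomes measures of adherence of participants to interventions", without tying this to the second comparison. Section 4.4.2 says "After completing a counseling session, participants in the TECC group will receive an online medical certificate".

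**The concern.** The definition does not match its label. The contrast drawn in section 4.6 is allocation against receipt, and grouping by receipt is an as-treated analysis. A per-protocol analysis restricts to women who received what they were allocated and does not move anyone between arms.

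The difference has a concrete route in this trial. Crossing over happens after randomisation, and the rule in section 5.3 applies only to the TECC arm. A woman who could not complete the session is taken out of the TECC group and added to the control group. If her chance of taking up LARC differs from that of other women, both groups shift, in opposite directions, and the comparison is biased even if TECC does nothing. A reader would also take the result for a per-protocol estimate and might read its agreement with ITT as support of a kind it does not give.

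**Working it through.** **The passages together.** (a) Section 4.6: the second comparison groups by intervention received. (b) Section 5.3: a TECC woman who cannot complete the session receives standard counselling. (c) Section 4.4.3: in-person counselling is the control care. From (b) and (c), the counselling such a woman received is the control intervention; from (a), she is counted with the controls. No single sentence says this, but nothing beyond these three sections is needed to reach it.

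**The plan's own figure.** No stated number is contested. For background, 12% against 24%, two-sided 5% and 90% power give 214 per arm with pooled variance and 211 with unpooled, so the stated 212 is reproduced.

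**Size of the bias: inputs.**
- Uptake of 12% in both randomised arms: the control rate in section 4.6, taken with no true effect.
- 1:1 allocation: section 4.3.
- 204 women analysed per arm per country: 510 / 2 = 255, less the 20% loss in section 4.6, is 255 × 0.80 = 204. The number affects the error rates below but not the risk ratios.
- *c*, the share of the TECC arm that crosses over, and *u*, the LARC uptake of those women: **not in the Protocol**. Assumed ranges are 2% to 20% for *c* and 4% to 20% for *u*.
- No cross-over from control to TECC is assumed.

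**Formulas.**
- As-treated TECC rate = (0.12 − *cu*) / (1 − *c*)
- As-treated control rate = (0.12 + *cu*) / (1 + *c*)
- With cross-overs excluded, the TECC rate is the same and the control rate stays 0.12.

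**One case in full**, *c* = 0.10 and *u* = 0.04: TECC = (0.12 − 0.004) / 0.90 = 0.1289; control = (0.12 + 0.004) / 1.10 = 0.1127. As-treated RR = 0.1289 / 0.1127 = 1.14. Excluded RR = 0.1289 / 0.12 = 1.07.

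**Risk ratios when the true value is 1.00 (as-treated / cross-overs excluded):**

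| Uptake in cross-overs | *c* = 2% | *c* = 5% | *c* = 10% | *c* = 20% |
|---|---|---|---|---|
| 4% | 1.03 / 1.01 | 1.07 / 1.04 | 1.14 / 1.07 | 1.31 / 1.17 |
| 8% | 1.01 / 1.01 | 1.03 / 1.02 | 1.07 / 1.04 | 1.15 / 1.08 |
| 12% | 1.00 / 1.00 | 1.00 / 1.00 | 1.00 / 1.00 | 1.00 / 1.00 |
| 20% | 0.97 / 0.99 | 0.94 / 0.96 | 0.87 / 0.93 | 0.75 / 0.83 |
| Women moved (204 × *c*) | 4 | 10 | 20 | 41 |

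The bias can go either way, and re-assigning the women distorts the ratio by roughly twice as much as excluding them.

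**Type I error** of the two-sided chi-square test (nominal 5%), from 400,000 simulated trials with 204 per arm, for *c* = 2%, 5%, 10% and 20%:
- *u* = 4%: as-treated 0.051, 0.058, 0.081, 0.179; excluded 0.050, 0.052, 0.059, 0.090.
- *u* = 8%: as-treated 0.051, 0.052, 0.058, 0.082; excluded 0.051, 0.050, 0.052, 0.060.
- *u* = 20%: as-treated 0.051, 0.056, 0.077, 0.167; excluded 0.050, 0.052, 0.058, 0.090.
- ITT: 0.049 to 0.050.

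**The case against.** The strongest case on the other side has four parts.

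- **The randomised comparison is intact.** ITT by allocation is named first, and nothing gives the second comparison a role in the decision. This stands, and it is why the point is minor.
- **The clause may be loose shorthand** for women who received their allocated intervention, with the full definition left to an SAP. The words do not say that. The Protocol does not leave the set undefined; it defines it in a way that contradicts the label. An SAP that copied the clause would carry the error forward, and one that corrected it would depart from the Protocol. If the shorthand was meant, the first option below simply writes it down.
- **The re-assignment is an inference.** The cross-over rule is a safeguard for the woman and was not written to define analysis groups. She may also have had part of a TECC session, and section 4.4.2 does not say whether the later TECC messages stop after cross-over, so what she received may be mixed. This is fair: the consequence is less certain than the mislabelling. It also shows that two analysts could build different data sets from the same clause.
- **The size rests on assumed inputs.** This stands. The largest distortions need 20% cross-over, while the Protocol requires a smartphone and English, supplies data at the clinic and runs a usability pilot first. The 204 is also debatable, since the 20% loss refers to 12 months and the primary outcome is at 12 weeks, but the risk ratios do not depend on it.

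**Conclusion.** The concern holds and is minor. Section 4.6 gives an as-treated definition under a per-protocol label, and on the literal text a TECC woman who crosses over under section 5.3 would be analysed with the controls. The size cannot be known from the Protocol. At 5% cross-over or less, with 4% to 20% uptake among these women, the risk ratio under no effect lies between 0.94 and 1.07 and the type I error is at most 6%. At 20% cross-over it could reach 1.31 or 0.75. If these women's uptake equals that of the others, there is no bias under no effect. The ITT result and the sample size are untouched.

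**What to change.** Change one sentence in section 4.6, in one of two ways.

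1. **Define per-protocol.** For example: *PP includes women who received their allocated counselling (TECC session completed; in-person counselling received), each kept in her randomised arm; women who crossed over are excluded and not re-assigned.* This roughly halves the distortion but does not remove it: the set is smaller and still open to selection (RR 1.04, 1.07 and 1.17 at 5%, 10% and 20% cross-over with 4% uptake). It needs receipt of counselling to be known in both arms. The adherence measures promised in section 4.1 should supply this, and for TECC the completion certificate leaves a record.
2. **Keep the grouping and relabel it** as as-treated and descriptive. This needs no new data.

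As a suggestion only, the same sentence could say that ITT is the basis for the conclusion and the other comparison a sensitivity analysis. The cross-over rule in section 5.3, the allocation and the sample size need not change.

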Effective contraception is a crucial part of sexual and reproductive health and rights (SRHR), women's empowerment and poverty reduction (1, 2). The periabortion period entails opportunities to provide women with choice and access to modern contraceptives. Long-acting reversible contraception (LARC) methods defined as hormonal intrauterine device (IUD), copper IUD and contraceptive implant, are particularly effective in reducing unintended pregnancies(3). Despite this, unmet need of postabortion contraception and underutilization of LARC remain high globally (4). Most contraception postabortion can be initiated immediately at the time of the abortion (all oral contraception, implant, injection as well as IUD after surgical abortion), whereas a delay of insertion of the IUD is recommended until a medication abortion is complete, a minimum of 1 week and in our study setting health care professionals (HCPs) often recommend 2-6 weeks.

The Covid-19 pandemic has exacerbated global inequity in access to care, particularly for women, and highlighted the potential of remotely provided care and counseling, i.e., telemedicine (5, 6). Telemedicine for abortion can circumvent barriers to access and minimize pressure on facilities, with similar clinical outcomes as in in-person care (7, 8). However, the feasibility, effectiveness, and optimal timing of TECC in the post/periabortion period remains to be investigated(9).

Among South African women, 66% report having had an unintended pregnancy in the past five years. There is low uptake of LARC methods particularly for the IUD which is used by only 3-4% of women using contraceptives in both South Africa and Kenya (10). Barriers to effective contraceptive uptake and use persist and include poor provider attitudes, lack of training in LARC insertion, long waiting hours, little or insufficiently individualized contraceptive counseling, and high rates of discontinuation(11).

Structured contraceptive counseling has been shown to improve uptake of LARC and reduce subsequent rates of unintended pregnancy(12, 13). However, not enough is known about optimal timing and format for postabortion contraceptive counseling in a low-income setting and no telemedicine interventions exist to answer to the unmet need of contraception after abortion.

[figure not shown]
3. Methodology PILOT STUDY

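### The primary comparison is fixed as unadjusted (chi-square test and csi risk ratio), so it cannot use the baseline contraceptive use already collected; it is valid but gives up a small, possibly nil, gain in precision

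*Protocol*

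**What the plan says.** Protocol section 4.6 sets the test: "Outcome data will be compared group-wise using Chi-square test according to intention to treat (ITT) among all randomized women according to allocation". It sets the estimate in the next sentence: "The risk ratio between groups of our main outcome and 95% confidence interval will be calculated using the STATA csi command". The only other role it gives to baseline data is a comparison of the arms to check the randomisation.

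Section 4.4.1 lists among the items of the baseline survey "reproductive history, prior and current use of contraception, and frequency of use of the internet". Previous use also enters one of the 12-week secondary outcomes, "choice or uptake of new method with regards to previous use", so the variable has to be collected and cleaned in any case.

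On the unit of analysis, section 4.6 says: "We also wish to be able to analyze our two study settings independently of each other". The sample size follows that wish, with 510 women per country. The natural reading is one estimate per country, although the csi sentence does not say which estimate is primary.

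On clinics, section 4.3 has South African women recruited at the abortion clinic and Kenyan women reached by telephone through a hotline. Under section 4.4.3 the Kenyan control group goes to "a clinic to which they are directed by the abortion care hotline (Kenya").

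**The concern.** The immediate command csi takes four counts and has no place for a covariate or a stratum; the chi-square test named beside it is unadjusted too. Because the protocol names both, this is a choice already made and not a detail left open. An adjusted primary estimate introduced later would depart from the protocol.

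A woman's earlier contraceptive use may well predict whether she takes up an IUD or implant. If it does, adjusting for it narrows the interval at no cost in recruitment. Section 4.6 places the start of clinical importance at a 5-point difference and expects the lower confidence limit to fall there, so each country has little slack. At stake is a small amount of precision, not the correctness of the result.

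**Working it through.** **Inputs from section 4.6.** Control uptake 12%, TECC uptake 24%, 212 analysed per arm, 90% power, 95% confidence (read as two-sided 5%).

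**The plan's own figures.**
- Women per arm, from the usual two-proportion formula: 211 (unpooled variance) or 214 (pooled). The stated 212 reproduces.
- Risk difference: SE = √[(0.12×0.88 + 0.24×0.76)/212] = √(0.288/212) = 0.0369. Half-width 1.96 × 0.0369 = 7.22 points. Lower limit 12 − 7.22 = 4.8%, which agrees with the stated 5% after rounding.
- Power of the uncorrected chi-square test at 212 per arm, by exact enumeration: 90.3%. A Wald test on the log risk ratio gives 89.9%, but that is not the planned test.

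**Assumed inputs.** The documents give neither the share of women with the baseline characteristic nor its association with uptake. Taken here: prevalence 10%, 30% or 50%; odds ratio in the control arm 1, 2 or 3; risk ratio 2.0 in every stratum.

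**One case by hand: prevalence 30%, odds ratio 3.**
1. Control risks of 8.14% (no baseline use) and 21.0% (baseline use) satisfy both conditions: 0.70×8.14% + 0.30×21.0% = 12.0%, and (0.21/0.79)/(0.0814/0.9186) = 3.0.
2. Between-stratum variance in the control arm: B = 0.3×0.7×(0.210 − 0.0814)² = 0.00347. With risks doubled, the TECC arm has 4B.
3. Stratification removes B + 4B. Half of B returns, because the risk difference itself varies between strata and the stratum mix is estimated from both arms. The net saving is 4.5B = 0.0156.
4. Relative saving: 0.0156/0.288 = 5.4%. The same steps at odds ratio 2 give 2.1%.

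**Simulation with Mantel-Haenszel estimates (40,000 trials per setting).** Reduction in risk-difference variance; a minus sign means the variance is larger.

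| Prevalence | OR 1 | OR 2 | OR 3 |
|---|---|---|---|
| 10% | −0.2% | 1.0% | 3.1% |
| 30% | −0.2% | 1.8% | 5.0% |
| 50% | −0.4% | 1.5% | 4.6% |

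A separate simulation with a standardised modified Poisson estimate gave −0.3% to 5.6% over the same grid. A fair summary is about 0.3% worse to about 5.5% better.

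**Consequence for the interval.** With a 5.5% cut, the half-width is 7.22 × √0.945 = 7.02 points and the lower limit 12 − 7.02 = 5.0%. With no gain it stays at 4.8%.

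**Consequence for power.** A stratified test set against the planned chi-square test changes power by about −0.2 to +1.4 points, that is from 90.3% to between about 90% and 91.7%.

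**Coding.** The only relevant prevalence in the documents is in section 2: "IUD which is used by only 3-4% of women using contraceptives in both South Africa and Kenya". For an indicator present in 3.5% of women, the simulated variance reduction is 0.1% at odds ratio 2 and 0.9% at odds ratio 3. Stratifying on IUD use alone would gain almost nothing.

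**Validity of the crude analysis.** Coverage of the crude 95% interval in simulation was 95.1% to 95.4%; that of the adjusted interval was 95.0% to 95.4%.

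**The case against.** The strongest case against is that nothing here is wrong. The crude comparison is valid, transparent and unambiguous, and it may lose nothing. Covariates are ordinary content for a statistical analysis plan, which is not at hand and could add an adjusted analysis. The benefit rests wholly on assumed inputs. The analysed number may also exceed 212, since the 20% loss is stated for 12 months while the primary outcome is at 12 weeks and records are searched for women who cannot be reached. At 255 per arm, crude power is already 94.4% and the lower limit 5.4%; a 5.6% variance cut would add only about 1.1 points. (At 204 per arm, which is 255 less 20%, crude power is 88.7%.)

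Most of this stands, and it caps the weight of the point. It does not remove it, because section 4.6 names the test and the estimator and so settles the matter in the protocol.

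Three stronger readings are tempting and are not supported:
- **That the unadjusted result is biased or its interval unreliable.** Randomisation protects it, and simulated coverage is nominal.
- **That adjustment would buy 1.5 power points or more.** That figure compares two Wald tests. Against the planned chi-square test the best case examined is about 1.4 points, and only if the test is changed as well. Replacing the estimate alone adds no power and could leave test and interval in disagreement.
- **That adjusting for clinic would give a clear further gain.** The documents give no clinic-specific uptake. In Kenya the clinic may be settled only after allocation, so it may not be a baseline variable there.

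**Conclusion.** The point holds as a minor efficiency matter to consider, not as an error. Section 4.6 fixes an unadjusted test and estimate and leaves unused a baseline variable that the trial collects anyway. Per country, at 212 analysed per arm and 12% versus 24%, the variance effect of using it runs from about 0.3% worse to about 5.5% better, with at most about 1.4 power points and 0.2 points on the lower confidence limit. These ranges assume baseline use in 10% to 50% of women, an odds ratio of 1 to 3 and a constant risk ratio of 2.0. The documents support none of these covariate values directly, and the gain may be nil. If both countries were pooled the question would hardly matter: at 408 per arm, crude power is already 99.4%.

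**What to change.** Amend the analysis paragraph in section 4.6 as follows.

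1. Within each country, make the primary risk ratio and risk difference Mantel-Haenszel estimates stratified by baseline contraceptive use, coded as any method versus none, and state which estimate is primary.
2. Replace the chi-square test of the primary outcome with the Cochran-Mantel-Haenszel test on the same strata, so that test and interval agree.
3. Add recruiting clinic as a stratum only where it is fixed before allocation, which is the case for the South African clinics.
4. Stratify any pooled estimate by country.
5. Keep the crude chi-square and csi results as supportive.

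The cost is one paragraph and slightly more programming, with no new data. The coding, including that of a missing baseline answer, must be fixed before outcome data are seen. If baseline use does not predict LARC uptake, the price is about 0.3% more variance, or about 0.2 power points.
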